Prilocaine, in particular, since its recent marketing into its stable hyperbaric form, has already been used for spinal injection in many studies in orthopedic surgery, gynaecologic surgery, and urologic surgery where it permitted a good quality nerve blockade with less secondary effects (14, 15). Its use, indeed, has shown a rapid onset anaesthesia (from 8 to 18 minutes maximum), a shorter action during time compared to the bupivacaine and a faster motor block offset in postoperative time, determined at 118 minutes (16).

In obstetrics, the former prilocaine isobaric form has been used only for epidural analgesia for the labour and vaginal delivery. Nevertheless, newborn high methemoglobinemia has been observed, due to long time epidural perfusion, at elevated doses in a range of 5,4-6,7 mg/kg (higher doses than 600mg) (17). Recently, hyperbaric prilocaine, without opioids adjuvants, has been used for c-section surgery in intrathecal injection in a pilot study realised to determine the efficacy dose 95 (ED95) (18). The results seem to be promising.

Until now, no study has ever compared prilocaine versus bupivacaine in spinal injection for c-section.

Our primary goal is to analyse the place of hyperbaric prilocaine 2% in a context of scheduled cesarean section by a power comparison study versus hyperbaric bupivacaine 0,5%, to find the most efficient one with a shorter action time and less secondary effects between this two local anaesthetics.

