2.3. Statistical analysis method

The primary outcome that will be analysed in this study is the time to motor block resolution after intrathecal injection of the two local anaesthetics.

Every patient will receive, after randomisation, a dose of local anaesthetic (bupivacaine or prilocaine); the study will be powered to highlight a difference of 20% for the principal variable between the groups.

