2.4.2. Central block (spinal injection)

- Sensitive block: level (pressure test, cold and pin-prick) every 2 minutes after spinal injection for 15 minutes, then every 5 minutes until the end of the surgery, then every 30 minutes until the complete release of the sensitive block (T12-S1) ;
- Time between spinal injection and reached of T4 level ;
- Obtained level 5 minutes after spinal injection ;
- Maximum sensitive level ;
- Complete lifetime of the sensitive block (as the period between maximun level and the regression to the level T12-S2) ;
- Lifetime of an adequate anesthesia for surgery (as the period between spinal injection and a VAS \geq 3 or a sensitive level superior regressed below T4 ;
- Lifetime of the complete anesthesia (as the period between spinal injection and a VAS \geq 0.
- Motor block: Modified Bromage score (from 1 to 6), before spinal injection, 10, 15, 20 minutes after injection, then every 15 minutes until the end of the surgery, then every 30 minutes until the complete released of the motor block (Bromage 6) ;
- Time of installation of the motor block (time between spinal injection and maximum motor block or Modified Bromage score of 1) ;
- Total lifetime of the motor block (time between maximal blockade/ Modified Bromage score 1 and a Modified Bromage score 6).

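### Motor-block installation time cannot be recorded below 10 minutes on the scheduled Bromage readings; how much this costs is unknown, and the primary outcome is not affected

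*Combined protocol and SAP*

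**What the plan says.** All of this is in the combined protocol and SAP.

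- **Motor readings (section 2.4.2).** The modified Bromage score is taken "before spinal injection, 10, 15, 20 minutes after injection, then every 15 minutes until the end of the surgery". Postoperatively the interval is half an hour, up to full motor recovery. The readings around onset therefore fall at 10, 15, 20 and 35 minutes.
- **Installation time (section 2.4.2).** It is defined as "time between spinal injection and maximum motor block or Modified Bromage score of 1".
- **Motor-block lifetime (section 2.4.2).** It is defined as "time between maximal blockade/ Modified Bromage score 1 and a Modified Bromage score 6", so it starts at the event that ends installation time.
- **Sensory readings (section 2.4.2).** The level is tested "every 2 minutes after spinal injection for 15 minutes, then every 5 minutes until the end of the surgery".
- **Primary outcome (section 2.3).** "The primary outcome that will be analysed in this study is the time to motor block resolution after intrathecal injection of the two local anaesthetics".
- **Onset background (section 1).** Prilocaine in other types of surgery "has shown a rapid onset anaesthesia (from 8 to 18 minutes maximum"). This refers to anaesthesia, not to motor block.

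No section schedules a Bromage score between injection and 10 minutes. None gives a rule for continuous observation, interpolation or censoring of installation time.

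**The concern.** A variable defined by when an event happens can be no finer than the readings that detect it. If installation time is taken from the scheduled scores, a woman maximally blocked at 2, 5 or 8 minutes gets the same value, 10. One blocked at 10.1 minutes gets 15, and one blocked at 21 minutes gets 35, which is 14 minutes late. The variable becomes a few tied values.

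Two things follow. A difference in speed of motor onset is compressed if both drugs act mostly before 10 minutes, and a null comparison could then reflect the schedule and not the drugs. Motor-block lifetime also starts late, by an amount that can differ between arms, because faster onset is rounded up further. The sensory level is being tested every 2 minutes over the same period, so the gap is not for want of an assessor.

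**Working it through.** **Inputs from the documents.** Motor readings at 10, 15, 20, 35, 50 minutes and so on (section 2.4.2); sensory readings every 2 minutes for 15 minutes (section 2.4.2); supine only after at least 5 minutes (section 2.2.2). The plan has no figure of its own for motor onset, so there is nothing to reproduce.

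**Assumptions.** Onset is normal with SD 2 minutes, and the mean is varied. Each onset is recorded at the first scheduled reading at or after it.

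**Formula.** With readings g1 < g2 < ..., mean m and SD s, the recorded mean is the sum over k of gk × [Φ((gk − m)/s) − Φ((g(k−1) − m)/s)], where the first bracket is Φ((10 − m)/s).

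**Example, means 6 vs 8.**
- Mean 6: Φ(2) = 0.977 are recorded at 10 and 0.023 at 15. The recorded mean is 10 × 0.977 + 15 × 0.023 = 10.11.
- Mean 8: Φ(1) = 0.841 at 10, 0.158 at 15, and a negligible share at 20. The recorded mean is 10.79.
- Recorded difference: 10.79 − 10.11 = 0.68, against a true 2.0. The shares tied at 10 minutes are 98% and 84%.

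| Assumed means (min) | True difference | Recorded difference | Start recorded late by, faster / slower arm |
|---|---|---|---|
| 6 vs 8 | 2.0 | 0.68 | 4.1 / 2.8 |
| 5 vs 9 | 4.0 | 1.52 | 5.0 / 2.5 |
| 8 vs 10 | 2.0 | 1.74 | 2.8 / 2.5 |
| 10 vs 12 | 2.0 | 2.01 | 2.5 / 2.5 |
| 12 vs 14 | 2.0 | 1.91 | 2.5 / 2.5 |

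**Effect on motor-block lifetime.** At 6 vs 8 the late start shortens the recorded lifetime by 4.1 − 2.8 = 1.3 minutes more in the faster arm. Against the 118 minutes that section 1 quotes for motor offset with prilocaine, that is 1.3/118, about 1%.

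**A second model.** Assume 50 women per arm (the ratio is not stated), log-normal onset with log-SD 0.4, one arm 20% faster, and a two-sided Mann-Whitney test at 0.05. Power with exact times is about 0.78. With the slower arm's median at 6, 8, 10 and 15 minutes, the share floored (slower/faster arm) is 90/97%, 71/87%, 50/71% and 15/32%. Power on the scheduled readings is about 0.27, 0.51, 0.66 and 0.74.

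**Would extra readings be enough?** The same normal model and formula were applied to two denser schedules.
- Adding only 6 and 8 minutes: a true 2.0 at 8 vs 10 is recorded as 2.7, because the spacing jumps from 2 to 5 minutes.
- Readings at 6, 8, 10, 12, 14, 15, 20, 25, 30 and 35: a true 2.0 is recorded as 1.7 at 6 vs 8, 2.0 at 8 vs 10, 2.1 at 10 vs 12, and 2.6 at 12 vs 14.

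Denser readings shrink the floor, but uneven spacing still distorts a comparison that takes the reading time as the event time. The analysis must use the interval.

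**The case against.** The case against is mainly one of weight, and much of it stands.

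- **The large losses come from chosen inputs.** A reader might take the 8-to-18-minute range in section 1 as evidence that prilocaine's motor block is often complete before the first reading. The documents do not support that: the range is for anaesthesia in non-obstetric surgery. If motor onset were uniform over it, only (10 − 8)/(18 − 8) = 20% would be floored, and with means of 10 minutes or more the mean difference is almost intact. This stands, and it is why the size must be left open.
- **Recording at 10 minutes is an inference.** Section 2.4.2 lists installation time as its own item and does not say it is read only from the scheduled scores. But no other source is described, so the floor is what the plan gives when followed as written.
- **The variable is peripheral.** Section 2.3 plans no test on it, motor onset is in neither the success nor the failure definition of section 2.2.2, and sensory onset is captured finely. This stands and limits the point to a minor one.
- **The end of motor-block lifetime is coarser than its start.** Postoperative readings are 30 minutes apart, against a late start of up to 10 minutes for onset before the first reading. This stands for precision, but a start delay that differs between arms is still a bias and is simple to avoid.
- **Early readings are awkward.** The woman is seated for at least 5 minutes, the catheter is placed after the injection, and blood pressure is taken every minute (section 2.4.4). This rules out a 4-minute reading and may cost some at 6 and 8. It does not explain a gap to 10 minutes.

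**Conclusion.** The point holds as a limited one. On the scheduled readings, installation time has a floor of 10 minutes and the recorded start of motor-block lifetime is late. That follows from section 2.4.2 alone, provided the variable is taken from the scheduled scores.

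The size is not known. Under the assumed normal model, a true 2.0-minute difference is recorded as anything from 0.7 (means 6 vs 8) to 2.0 (10 vs 12). The loss is material only if many women are maximally blocked before 10 minutes, and the documents do not say whether they are.

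Two stronger conclusions should not be drawn. One is that the drugs cannot be compared on motor onset: that would need most women at the floor, which nothing in the documents shows. The other is that the primary outcome is biased: section 2.3 times it from injection, so neither the floor nor the late start enters it.

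**What to change.** In section 2.4.2:

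1. Once the woman is supine, record the modified Bromage score at the sensory readings already scheduled at 6, 8, 10, 12 and 14 minutes, keeping 15 and 20. Do not schedule one at 4 minutes, when she is still seated.
2. Add readings at 25 and 30 minutes if maximum block has not been reached by 20.

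In section 2.3:

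3. State that installation time is analysed as interval-censored between consecutive readings. A woman at Bromage 1 at her first reading is blocked by that time, not at it. The simpler alternative is to report the proportion at maximum block by 10, 15 and 20 minutes.
4. Compare motor-block duration from injection, not from recorded maximal block.

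The cost is probably a few extra seconds per reading in a busy period, with some early readings missed during catheter placement and positioning. Interval censoring accommodates missed readings. If the extra readings prove impractical, items 3 and 4 need no bedside change and remove the main risk of misreading the result. No treatment is altered.

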2.2.3. Postoperative

- Postoperative analgesia : Paracetamol + NSAID at the end of the surgery.
- Removal of the urinary catheter : after complete offset of the motor block and a stand up trial (after a forced extention of the legs against resistance, about 3 hours after the intrathecal injection) ; and/or S2 level restored.
- Monitoring of the bladder volume 1x/hour, by Bladderscan examination until first miction.

In case of bladder retention, defined such as a bladder volume higher than 600ml, associated at a spontaneous miction, a bladder catheterisation will be realised.

- Walking : it will be asked to the patient to do a walking test (6 minutes walking test) with a minimum of 25 m to walk, 1h, 2h, 3h and 4h after a complete released of the motor block and a sensitive block lower than L5-S1.

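### Is the primary outcome left undefined because 2.3 counts from injection while the listed motor-block duration starts at maximal blockade?

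*Combined protocol and SAP*

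**What the plan says.** Section 2.3 names the primary outcome as "time to motor block resolution after intrathecal injection of the two local anaesthetics" and adds that "the study will be powered to highlight a difference of 20% for the principal variable between the groups". Section 2.1 sets the total at 100 women.

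Section 2.4.2 gives the Modified Bromage schedule. After a reading before injection, scores are taken "10, 15, 20 minutes after injection, then every 15 minutes until the end of the surgery". For the postoperative period, the spacing widens and the rule reads "then every 30 minutes until the complete released of the motor block (Bromage 6").

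The same section lists two motor intervals:

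- onset: "Time of installation of the motor block (time between spinal injection and maximum motor block or Modified Bromage score of 1")
- duration: "Total lifetime of the motor block (time between maximal blockade/ Modified Bromage score 1 and a Modified Bromage score 6")

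Section 2.2.3, in its rule on removing the urinary catheter, also mentions motor recovery: "after complete offset of the motor block and a stand up trial (after a forced extention of the legs against resistance"). The rule places this at "about 3 hours after the intrathecal injection".

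**The concern.** A reader who goes from 2.3 to the data list looks for a variable running from injection to full motor recovery and finds none under that description. The nearest candidate starts its clock at maximal blockade. The two differ by the onset time, so any difference in onset between the drugs would move the treatment effect minute for minute. Section 2.3 does not itself name the score that counts as resolution, and the catheter rule in 2.2.3 describes motor recovery in different terms.

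The reading interval adds to the unease. After surgery the score is read every 30 minutes, while a 20% difference on the documents' own time scale is itself about 24 to 36 min. If resolution can be dated in more than one way, the result might seem to depend on a choice made after the data are seen. At stake would be the size, power and false-positive rate of the trial's single primary comparison.

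**Working it through.** **1. Is the primary defined?** Set the sections side by side.

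- Status and start: 2.3 labels the outcome as primary and starts it at intrathecal injection.
- End: 2.4.2 treats Bromage 6 as full release of the motor block and continues readings until it is reached.
- Derivation: let *O* be the listed onset (injection to maximal block) and *L* the listed duration (maximal block to Bromage 6). Then *O* + *L* = time from injection to Bromage 6, which is the 2.3 outcome. It can also be read directly from the time of the Bromage 6 reading.
- The rule in 2.2.3 governs the catheter. It requires motor recovery together with a stand-up trial, and it does not define the endpoint.

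**2. Inputs for the size of the dating effect.** The plan's total of 100 cannot be reproduced, because alpha, power and SD are not stated. With 50 per arm (1:1 assumed), two-sided 5% and a 20% difference, the implied coefficient of variation (CV) is 0.2 / [(1.960 + 0.842) × √(2/50)] = 0.357 for 80% power, and 0.2 / [(1.960 + 1.282) × 0.2] = 0.308 for 90%.

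Two pairs of means are assumed:

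- 118 min, cited in the Introduction for prilocaine, as the shorter arm: 118/0.8 = 147.5, difference 29.5 min.
- The 3 hours in 2.2.3, assigned to bupivacaine by assumption: 180 v 144, difference 36 min.

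Taking 20% of 118 instead gives 23.6 min.

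**3. Dating at the first reading of 6.** With 30-minute readings the average delay is 30/2 = 15 min in each arm.

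- Absolute difference: (147.5 + 15) − (118 + 15) = 29.5 min, and (180 + 15) − (144 + 15) = 36 min. Both are unchanged.
- Relative difference: 29.5/162.5 = 18.2%, and 36/195 = 18.5%.
- Added variance: 30²/12 = 75 min² per woman. At CV 0.35 with 147.5 v 118, the SDs are 51.6 and 41.3. The standard error goes from √[(51.6² + 41.3²)/50] = 9.35 to √[(51.6² + 41.3² + 150)/50] = 9.51. Approximate power goes from Φ(29.5/9.35 − 1.96) = 88.4% to Φ(29.5/9.51 − 1.96) = 87.3%.

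A simulation of the 2.4.2 schedule agrees. It used log-normal times, a t-test, 20,000 runs and an assumed surgery end of 50 to 80 min.

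| CV 0.35 | Exact time | First reading | Midpoint |
|---|---|---|---|
| 147.5 v 118 | 88.4% | 86.8% | 86.9% |
| 180 v 144 | 88.9% | 88.1% | 88.2% |

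Across CV 0.17 to 0.35, type I error is 4.7% to 5.0%, the absolute difference moves by at most 0.5 min, and the recorded relative difference is 17.8% to 18.5%. First-reading and midpoint dating disagree on significance in at most 0.9% of trials. This is expected: where every interval is 30 min, the midpoint is the first reading minus 15 min for every woman, so the t statistic is the same.

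**4. What would follow if the listed duration replaced the primary?** The difference becomes the true difference minus the onset gap. With prilocaine onset 5 or 10 min earlier (assumed), 29.5 becomes 24.5 or 19.5 min, and 36 becomes 31 or 26 min. At CV 0.35 and standard error 9.35, power is Φ(24.5/9.35 − 1.96) = 74.6% or Φ(19.5/9.35 − 1.96) = 55.0%. If bupivacaine were the earlier drug, the difference would rise to 34.5 or 39.5 min. With equal onset nothing changes.

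**The case for a change.** The best case for acting is that this is the trial's only primary outcome and the fix would be two sentences. The listed duration resembles the primary closely enough for an analyst to pick it up by mistake or by choice. If that happened and onset differed, the damage could be real. Besides the power loss shown above, a 10 min onset gap with no true difference from injection would make the listed duration significant in 12.6% to 50.6% of simulated trials across CV 0.17 to 0.35, against a nominal 5%.

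The textual facts stand: neither listed interval alone equals the primary, and no dating rule is written. The arithmetic also stands. As evidence of harm it fails, because two things must happen together. The analyst must depart from what 2.3 says will be analysed, and motor onset must differ between drugs by an amount the documents do not give. The 8 to 18 min in the Introduction is a range for onset of prilocaine anaesthesia and says nothing about motor onset by arm. With early readings at 10, 15 and 20 min, a 10 min gap in recorded onset would mean one arm at 10 and the other at 20, with no spread within either. The 50.6% also needs CV 0.17, well below the 0.308 to 0.357 that a total of 100 would imply at 90% to 80% power.

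**Conclusion.** No change follows. Read together, 2.3 and 2.4.2 give one primary: injection to Modified Bromage 6. The readings needed to compute it are already planned. The listed duration from maximal blockade is a component of it and does not compete with it. The missing dating rule is a detail that analysts fill sensibly, either with the first reading of 6 or with the midpoint. First-reading dating lengthens both arms by about 15 min and shows a true 20% as about 18%. The 20% is a powering target, so no decision turns on that shift. The simulated power cost at CV 0.35 is 1.6 points or less, and midpoint dating recovers essentially none of it.

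These sizes rest on 50 per arm, a two-sided 5% t-test, the assumed means and CVs, and the same reading schedule in both blinded arms. A clarifying line naming the end score and the dating convention would be harmless, but it would not improve the primary comparison. The unstated alpha, power and SD behind the total of 100 are a separate matter.

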2.4.3. Surgical variables

- Time between spinal injection and skin incision ;
- Time between spinal injection and placental delivery ;
- Time between skin incision and placental delivery ;
- Time between uterine incision and placental delivery ;
- Lifetime of the surgery.

2.4.4. Haemodynamic variables

- BP (BP/ 1' for 15 minutes, then BP/2,5' until the end of the surgery, BP/20' in the awaking room), CF ;
- Needs of vasopressors drugs, total dose of administrated vasopressor drugs (phenylephrine, ephedrine).

2.4.5. Ventilation, state of consciousness

- SpO₂, respiratory frequency, situation of respiratory depression (RF $<$ 10c/minutes or SpO₂ $<$ 95%) ;
- State of consciousness every 10 minutes after the spinal injection for one hour.

2.4.6. Secondary effects

- Pain: VAS at incision time, placental delivery time, peritoneal closing time, skin closing time and every 5' during the c-section, then every 4 hours for 24h ;
- Nausea/ Vomiting, Headache, Prurit from 15 minutes after spinal injection, then every 4 hours for 24h ; marked as : 0= no symptoms ; 1= symptoms with no treatment necessary ; 2= Symptoms present and treated ;
- Total blood loss (ml) ;
- Transient neurologic symptoms at D0, D1, D3 and D15, Defined as pain or dysesthesia or both, showed after complete released of the block in the lower limbs (19).

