1. INTRODUCTION

In case of scheduled cesarean section, intrathecal anaesthesia, in the absence of contraindications, is the choice of anesthetic technique (1). This procedure is simple to perform and involves the administration of local anaesthetic with or without adjuvant, into the subarachnoidal space surrounding the spinal nerves and the spinal cord. It leads to a rapid onset of surgical anesthesia with a good quality motor and sensory nerve block to let the surgeons do their surgery in good conditions as well for the patient (2). So, it allows the parent, the mother in particular, to have a better experience of the delivery during the c-section.

Nevertheless, there are secondary effects due to this procedure and the local anaesthetics. Principally, haemodynamics effects such as major low blood pressure can decrease the utero-placental perfusion and cause nausea and vomiting (3,4). The outcome of the newborn is essentially related to the duration of maternal hypotension (5,6). Some prophylactic measures or treatments are taken, such as preloading perfusions, mother's position (left tilt) and the use of vasopressors drugs (ephedrine, phenylephrine) (3,4,7), but their efficacy remains questionable (8). Today, the studies' authors agree on the fact that the haemodynamics effects of the intrathecal injection are directly linked to the dose of the local anaesthetic (9).

For over 30 years, hyperbaric bupivacaine 0,5%, an amide-type local anesthetic of long action time, is the most used drug for spinal injection in c-section, associated to opioids (sufentanil or fentanyl and morphine) (10,11). However, its use is frequently followed by haemodynamical instability and by a motor nerve block of long duration, two factors that lead to an increased foetal risk and maternal discomfort (12).

The arrival on the market of newer short and intermediate duration time local anaesthetics such as chloroprocaine and prilocaine, seems to offer a good alternative for hyperbaric bupivacaine (13). This coincides with practice trends in anaesthesia for more ambulatory perioperative pathways and to a fast track rehabilitation in every speciality, obstetrics included.

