2.2.2. Peroperative

- Monitoring :

ECG, NIBP, pulse oximetry (SpO2), peripheral venous access 18G or 16G, urinary catheter, Bair hugger.

- Realisation of the combined anaesthesia :

Vascular co-loading with 1000ml of Hartmann solution.

The patient is in a sitting position, L3-L4 level is localised. With a Vygon combined anaesthesia set, the epidural space is reached with a Tuohy 8 cm needle, 17G with a low resistance syringe filled with saline. Then, a 29G needle is used through the Tuohy needle to access to the spinal space ; once the cephalo-spinal liquid reflux is positive, the test solution with 100 µg of morphine is injected into the spinal space in approximatively 20 seconds. Then an epidural multiperforated catheter is introduced until 3-4 cm in the epidural space, an aspiration test is done but no test dose is injected. The patient is placed, after 5 minutes minimum of the intrathecal injection, in supine position with a left tilt and 3l/min of nasal O2.

Every patient receive, after randomisation, a predetermined local anaesthetic dose (bupivacaine or prilocaine).

- Nerve blockade evaluation :

The evaluation of the sensitive level will be realised by a *pressure test*, a *cold test* and a *pin-prick test*.

The block will be considered as a :

- **SUCCESS** : bilateral T4 level reached in 15 minutes after intrathecal injection without additional epidural injection needed within 45 minutes peroperative ; no pain at the skin incision, no pain during 45 minutes after the skin incision.
- **FAILURE** : level < T4 at 15 minutes after the intrathecal injection or the additional epidural injection needed during the cesarean section (*lidocaine 2% with epinephrine*) by 5ml/5minutes for a VAS< 3.

- Low blood pressure evaluation :

As low blood pressure, we define a blood pressure lower than 20% or more than the basal blood pressure (Systolic BP before spinal anaesthesia).

Treatment : *Ephedrine 5mg/ml, phenylephrine 100 µg/ml* by titration (ml by ml); blood pressure goal : Systolic BP before spinal injection -10%.

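### Nausea and vomiting are recorded only from 15 minutes after the spinal, with no stated look-back, so an episode confined to the first 15 minutes has no scheduled record

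*Combined protocol and SAP*

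**What the plan says.** Section 2.4.6 of the combined protocol and SAP sets the schedule: "Nausea/ Vomiting, Headache, Prurit from 15 minutes after spinal injection, then every 4 hours for 24h". Each symptom is graded 0, 1 or 2 according to presence and need for treatment, the top grade being "Symptoms present and treated". No reference period is attached to any score.

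No other section schedules a nausea or vomiting score or an antiemetic record. The drug record in section 2.4.4 covers vasopressors only.

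Other variables are followed closely from the injection onward:

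- Section 2.4.4, blood pressure: "BP (BP/ 1' for 15 minutes, then BP/2,5' until the end of the surgery".
- Section 2.4.2, sensory level: "every 2 minutes after spinal injection for 15 minutes, then every 5 minutes until the end of the surgery".
- Section 2.4.5: "State of consciousness every 10 minutes after the spinal injection for one hour".

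The Introduction supplies the link between pressure and symptom: "haemodynamics effects such as major low blood pressure can decrease the utero-placental perfusion and cause nausea and vomiting". It also makes tolerability part of the aim, which is to find the more efficient drug "with a shorter action time and less secondary effects between this two local anaesthetics".

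**The concern.** By the protocol's own reasoning, a fall in pressure after the spinal is a route to nausea and vomiting. The plan watches pressure most densely in the first 15 minutes, yet sets the start of the symptom record at the end of that window. A patient who is nauseated at minute 6 and well by minute 12 could then be scored 0 throughout.

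At stake is the completeness of one secondary outcome that bears on a declared aim. Early symptoms cannot be rebuilt afterwards from the pressure or vasopressor records, because neither of them records symptoms.

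**Working it through.** The plan states no figure on this point that could be reproduced. The check sets the schedules side by side and then asks what follows under each reading of the line.

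**Step 1. Scheduled observations after the injection and strictly before minute 15.**

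| Variable | Section | Times (minutes) | Count |
|---|---|---|---|
| Blood pressure | 2.4.4 | 1, 2, ..., 14 | 14 |
| Sensory level | 2.4.2 | 2, 4, ..., 14 | 7 |
| Motor block | 2.4.2 | 10 | 1 |
| Consciousness | 2.4.5 | 10 | 1 |
| Pain | 2.4.6 | tied to incision and surgery, no fixed clock time | not countable |
| Nausea/vomiting | 2.4.6 | none | 0 |

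Counting minute 15 itself would make 15 blood pressure readings. These counts locate the gap; they do not measure how much nausea data is lost.

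**Step 2. Nausea and vomiting scores over 24 hours.** Read as single scores, the line gives 15 minutes and then 4, 8, 12, 16, 20 and 24 h, which is 1 + 24/4 = 7 scores. If the 4-hour steps run from the 15-minute score instead, the later times shift by 15 minutes and the count is still 7. Either way none falls before minute 15.

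**Step 3. What happens to an episode confined to minutes 0-15.**

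- The 15-minute score looks back to the injection: the episode is captured.
- The 15-minute score describes that moment only: the episode has no record.
- Recording is continuous but starts at minute 15: the episode has no record.

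The text does not choose among these readings. The stated start time fits the second and third more naturally than the first.

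**Step 4. Can the effect on the comparison be derived?** Let p be the true proportion of patients with nausea or vomiting in an arm, and L the share of those whose symptoms fall only in minutes 0-15. With no look-back the recorded proportion is p(1 - L). For arms A and B:

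recorded difference - true difference = [pA(1 - LA) - pB(1 - LB)] - (pA - pB) = pB x LB - pA x LA.

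- If LA = LB = L, the absolute difference is multiplied by (1 - L) and the risk ratio is unchanged.
- If LA and LB differ, the error can have either sign.

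The documents give no incidence or timing of nausea for either drug, so none of pA, pB, LA and LB is known. I put in no assumed values, because the result would only reflect the values chosen.

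**The case against.** The strongest reply is that this is a missing phrase and not a missing observation. A grade that distinguishes treated from untreated symptoms normally needs knowledge of what happened before the moment of scoring, so the 15-minute score may be meant as a summary since injection. A case report form, which is not among the documents, could say so. That possibility stands, and under it little or nothing is lost. It does not remove the point: no section states it, the explicit start time points the other way, and staff at two centres could read the line differently.

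Other limits also stand. The schedule is the same in both arms of a trial described as double-blinded. Headache and pruritus share the same start, and pain has no fixed clock time in the window, so nausea is not a lone anomaly.

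A reader might also infer that the plan requires the block to be complete in this window. It does not. In section 2.2.2 "bilateral T4 level reached in 15 minutes after intrathecal injection" is one criterion for calling a block a success, and a lower level at that time is classed as a failure.

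A reader might extend the gap from minute 15 to the first 4-hourly score. That holds only if the line means isolated scores without look-back. It can equally be read as continued recording from minute 15, so the documents do not establish the later gap.

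**Conclusion.** The point holds in a limited form. As written, the plan has no scheduled record of nausea or vomiting that begins and ends in the first 15 minutes after the injection: 0 scores, against 14 blood pressure readings and 7 sensory tests. This rests on taking section 2.4.6 literally, without an unstated look-back.

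It would be tempting to conclude that episodes will be lost, or that the comparison is biased for or against prilocaine. The documents support neither: they do not exclude a look-back, and they give no incidence or timing from which to derive a number missed, a size or a direction.

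The primary outcome, time to motor block resolution (section 2.3), is unaffected, as are the blood pressure and vasopressor records. Severity is minor. The case for changing the line is that the improvement costs almost nothing.

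**What to change.** In section 2.4.6, start the nausea and vomiting record at the intrathecal injection, on the existing 0/1/2 grade. State that the 15-minute score covers the time since injection and that each later score covers the time since the previous one.

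The number of scores per patient stays at 7, so no extra observation is needed. The cost is one changed line on the record form. Recorded early rates may be higher than under the present wording; whether they will be cannot be told from the documents, and they would change little if staff already look back. Headache and pruritus can stay on the present schedule. The change concerns recording only and touches no treatment rule.
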